3.1 SYNOPSIS

Title:	Keeping in Touch with Youth as they Transition Through Type 1 Diabetes Care: A randomized control trial comparing the effectiveness of an eHealth text message-based intervention in conjunction with usual T1D care compared to usual care alone on diabetes self-efficacy
Study Description:	A multi-center, 1:1 randomized control trial with 6 sites (4 in Ontario and 2 in Quebec)
Objectives:	Primary Objective: Diabetes self-efficacy (SEDM) Secondary Objectives: Transition readiness (READDY), Barriers to Diabetes Adherence (BDA) Stigma subscale, HbA1c, healthcare utilization and cost of implementation Exploratory Objectives: embedded process evaluation
Endpoints:	Primary Endpoint: SEDM at 12 months Secondary Endpoints: READDY, BDA Stigma subscale, diabetes-related admissions and emergency department visits, HbA1c, cost of implementation data and LLM chatbot data. Exploratory Endpoints: qualitative and quantitative data from embedded process evaluation
Study Population:	234 (117 in each arm) adolescents with T1D preparing to transition to adult diabetes care and receiving care for T1D at participating pediatric centres in Ontario or Quebec; English or French speaking and possess their own mobile device that can send and receive SMS messages
Description of Study Intervention:	Text-message based algorithm that operates similar to a chatbot and will send SMS messages for T1D personalized support, education, resources and collection of outcome measures.
Study Duration:	21 months of recruitment and 12-month intervention period
Participant Duration:	12 months for each participant to complete the study

4 STUDY DESIGN

4.1 OVERALL DESIGN

First, we **hypothesize** that the intervention will improve diabetes self-efficacy.

We will conduct a **multi-site randomized control trial** to evaluate the effectiveness of an eHealth solution for T1D transition care. The study sample size is 234 adolescents with T1D from 6 pediatric diabetes centres (4 in Ontario and 2 in Quebec) and allocate them 1:1 to the intervention or control arm stratified by site. Participants will be recruited at their pediatric centre within 3-4 months of either their planned final pediatric visit or 18th birthday. We opted for individual randomization the target of the intervention is diabetes self-efficacy during the time between pediatric and adult care and relates to the individual rather than provider or clinic-based practices.

Intervention: both intervention and control groups will receive usual diabetes care including all medical visits and tests. In addition, the intervention group will receive the text messages for diabetes support and resources tailored according to their needs and interest. Both intervention and control groups will also complete PREMs and PROMs at baseline, 6 and 12 months.

Process Evaluation: the embedded process evaluation involves a mixed-methods approach using individual semi-structured interviews alongside user engagement metrics and quantitative outcome data to evaluate how and why the intervention achieved (or failed to achieve) the desired effects and identifying the different paths of engagement (i.e., combinations of KiT components) that produce a positive effect on trial outcomes. Using an embedded single case design with cross case synthesis, the objective of the process evaluation is to gain an in-depth understanding of whether the intervention was received as intended (intervention fidelity), the mechanisms of action, and the conditions and factors associated with initial engagement and sustained use of the intervention.

Health system impact: We will examine health care utilization of patients with T1D using de-identified administrative and, self-reported health data for at least 12 months after study enrolment. We will securely link patients' health card number to provincial administrative databases housed at ICES in Ontario and Med-Echo and Régie de l'assurance maladie du Québec (RAMQ) databases in Quebec.

4.2 SCIENTIFIC RATIONALE FOR STUDY DESIGN

We chose to conduct a multi-site randomized control trial in both Ontario and Quebec in order to ensure representation across the two main sizes of pediatric diabetes centers (tertiary and community); our intervention will also be available in both English and French; participants in both provinces will be able to select their preferred language of intervention delivery at study enrollment. We opted to do 1:1, individual level randomization because the target of the intervention is individual level diabetes self-efficacy during the time between pediatric and adult diabetes care and not pediatric provider or clinic-based transition care. The treatment allocation not being blinded to the research team will not pose any bias or contamination as randomization to control or intervention group will be completed via an automated computer program on REDCap; the randomization sequence will be generated by a biostatistician who is not involved in recruitment or enrollment and has no contact with study participants. The research team does not know the randomization sequence which will be in blocks of 2 or 4, thus making it difficult to pre-determine treatment allocation during the recruitment or consent process. This study is not blinded and therefore the research team, Memotext and participant will know which arm they have been randomized to. Also, the control group not having access to the tailored support or diabetes resource messages will not pose any potential problems or issues as the control group and

intervention group will both be receiving the regular standard of care for diabetes and will not be restricted access to their usual diabetes resources and supports. Both the control and intervention group will receive the same incentives to complete the outcome measures at baseline, 6 months, and 12 months. The Intervention group participants may receive compensation for participation in the process evaluation upon completion of the interview.

4.3 END OF STUDY DEFINITION

The end of the study is defined as completion of the 12-months in the intervention period and completion of at least the SEDM at 12-months. It is estimated that it will take 30 months from when the study opens to enrollment until the end of the study.

5 STUDY POPULATION

5.1 INCLUSION CRITERIA

To be eligible to participate in this study, an individual must meet all of the following criteria:

1. Diagnosed with type 1 diabetes, ascertained from patient's medical chart
2. Receiving out-patient care for T1D at a pediatric diabetes center participating in this study
3. Is within 6 months of either planned transfer or 18th birthday so research coordinator can approach patient and inform them about the study, and then can be re-approached for consenting and enrollment only within 3-4 months of either: planned transfer to adult diabetes care OR 18th birthday
4. Proficient in written and spoken English or French
5. Possession of their own personal mobile device that can support SMS with capacity to send and receive SMS/texts
6. Valid and working mobile phone number
7. Valid email address

5.2 EXCLUSION CRITERIA

An individual who meets any of the following criteria will be excluded from participation in this study:

1. Unable to carry out their diabetes care independently due to an intellectual or neurocognitive disability; discerned from medical chart during pre-screening
2. Non-resident of Ontario or Quebec
3. Planning to move out of either province in the next 6-12 months and after moving, will not be receiving diabetes care in either province and/or will not have a valid and working mobile number
4. Currently enrolled in any other clinical research trial with an SMS-based intervention
5. Currently enrolled in another diabetes intervention trial that will continue beyond the final pediatric diabetes visit

5.3 SCREEN FAILURES

Screen fails are defined as participants who consent to participate in the clinical trial but are not subsequently randomly assigned to the study intervention or entered in the study. A minimal set of screen

failure information is required to ensure transparent reporting of screen failure participants. Minimal information includes demography, screen failure details and eligibility criteria.

5.4 STRATEGIES FOR RECRUITMENT AND RETENTION

Sample size: The total target sample size for this trial is 234 adolescents with T1D, with 117 participants in each arm (intervention and control arm). Participants will be recruited from participating pediatric diabetes centers in Ontario and Quebec: four pediatric diabetes clinics in Ontario and two in Quebec. Recruitment will occur for 21 months while the intervention will occur for a 12-month period.

- Ontario (4 sites total): Two sites will be tertiary hospitals - The Hospital for Sick Children and the Children's Hospital of Eastern Ontario (CHEO), and the other two sites will be community hospitals – Oak Valley Health previously Markham Stouffville Hospital and Trillium Health Partners.
- Quebec (2 sites total): Two tertiary sites: Montreal Children's Hospital and CHU Saint Justine.

Recruitment, consenting and onboarding process: At each participating site in Ontario and Quebec, the following recruitment process will occur:

- 1) Local coordinator will identify eligible patients by pre-screening daily or weekly diabetes clinic lists and medical charts for inclusion and exclusion criteria. The local coordinator will obtain prior permission to access diabetes clinic lists from REB and site-specific institutional approval.
- 2) Initial contact with eligible patients:
 - a. Where applicable, a study introductory letter from the local diabetes team (circle of care) will be sent (via email or post-mail) to potentially eligible patients after pre-screening. The introductory letter will inform the patient of the research study (study objective and purpose, study tasks and duration of study), and will inform participant that they are eligible to participate. The study information letter will ask the participant to reach out to their local study coordinator via telephone or email if they are interested in participating. The letter will also allow an opt-out feature where patients can opt-out of being contacted about the study by calling, writing or emailing the contact provided to let the research team know. The letter will also indicate that if there is no response to the letter within 2 weeks of receipt, a member of the study team will reach-out to the patient via phone, email or in-person at their next diabetes clinic visit to explain the study and gauge interest in participation. If via telephone or email, the study team will attempt to contact the eligible patient up to a maximum of 3 times with 1-week in between each contact attempt.
 - b. If (a) is not feasible or permissible at a local site, the local diabetes team (circle of care) will send an opt-in letter (via email or post-mail) to all potentially eligible patients at their site. The opt-in letter will also provide the same details about the study as the Study Introduction letter in (a) but in (b), patients will be required to respond to the opt-in letter to express their consent to being contacted about this study by the local research coordinator either by phone, email, or in-person at their next diabetes clinic visit.
- 3) Other methods of advertising for this study: study flyers and digital advertisements will be posted on diabetes clinic waiting areas and waiting areas digital screens, with the contact information for the local research coordinator; we will also distribute study flyers in newsletters, communication boards, websites, and social media feeds.
- 4) Two weeks after initial contact from the circle of care, eligible patients (who have expressed interest from (2a) or did not respond to the letter from (2a) or opted-in from (2b) will be approached by the local research coordinator at their diabetes clinic visit or via telephone, video visit, or email to introduce the study again, provide a study information either in hard copy or electronically and discuss interest in participating in the study. The local research coordinator will explain study details

including purpose, study tasks, duration of study, responsibilities of participating in the study, risks, and benefits of participating in the study, study confidentiality, types of data that will be collected and what data elements will be shared with other members of the research team (and who these team members are), and planned use of participant data and data analysis. Sufficient time will be provided to answer any questions from the potential participant.

- 5) After reviewing the informed consent form, if a patient expresses interest in participating in the trial, the local research coordinator will email them a link to a site-specific informed consent form on REDCap, or will provide a hard copy version of the consent form. Local coordinators will explain all sections of the informed consent form to the patient and allow time for questions. When the patient is ready to provide consent, they will be instructed on checking off appropriate sections of the consent form electronically or on hard copy, and on providing their electronic signature on the electronic consent form or wet signature on hard copy of consent form.
- 6) Once a completed electronic or hard copy consent form is returned, the local coordinator will obtain relevant demographic and PHI information from the participant and confirm this information with participant, including: First and Last Name, DOB, OHIP # or RAMQ #, mobile phone number, mailing address including 6-digit postal code, and email address. This information will be kept on a site-specific enrollment log that is not stored on REDCap and will not be shared with other members of the study team.
- 7) The local coordinator will assign a site-specific study ID number to consented participant.
- 8) The local coordinator will randomize the participant using REDcap's automatic randomization feature. Both the local coordinator and participant will be aware of what study arm they were assigned to as local coordinator will need to explain next steps to the participant depending on study arm and participant will be aware of whether they will receive texts from the KiT intervention.
- 9) Upon randomization, the local coordinator will enter the randomized participant study ID number, randomization arm, mobile phone number, and preferred language in the Research Assistant Participant Enrollment form via Memotext.
- 10) Memotext will send an initial SMS to the participant's mobile phone number, letting them know they are now enrolled in KiT.
 - i. The following SMS will include the first URL link to a REDCap survey that first prompts to participant to complete the baseline KiT survey (demographic information and information about the participant's diabetes care and self-management). When this questionnaire is completed and submitted, the survey will automatically produce the next surveys for participant completion, one at a time: READDY tool questionnaire, SEDM, and BDA Stigma subscale
 1. Some of the content and sequence of the messages and resources sent to the intervention participants will be personalized, based on confidence ratings as measured by the "Readiness of Emerging Adults with Diabetes Diagnosed in Youth" (READDY) tool.
 2. For all participants, if they do not complete the questionnaires within 1 week of receipt, KiT intervention will send a follow-up reminder SMS asking them to complete the questionnaire. This reminder will be sent a maximum of two times (1 week apart). At week three, the local research coordinator will be notified via email by Memotext that the participant has not yet completed their questionnaires and will then follow up with the participant via telephone, SMS or email asking them to complete the questionnaires.
 3. Once the participant completes the questionnaires, they will be sent their \$20 Amazon gift-card via SMS.
 - ii. If the participant is in the intervention arm, after they complete the baseline questionnaires, they will then be sent an SMS with a link to a short enrollment survey where they will learn how to use KiT, access the settings, set up their frequency preferences to receive the content, and set up appointment reminders.

iii. Once the enrolment survey is completed, the intervention will begin for those participants.

11) KiT will continue to send SMS messages throughout the duration of the study (12-month intervention period) to individuals in the intervention arm. In addition to personalized SMS about T1D care and management that will be sent to intervention group, both study groups will receive SMS messages of URLs that will link to REDCap for the PREMs and PROMs at 6 months and 12 months from the date of enrolment.

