1 PROTOCOL SUMMARY

1.1 SCHEMA

Prior to Enrollment (21 month Recruitment Period)

Total 234: Screen potential participants by inclusion and exclusion criteria, obtain informed consent, Assign Study ID number

Randomize on REDCap (done by local coordinator)

KiT intervention arm (117 participants)

Control arm (117 participants)

Baseline

Local coordinator: securely transfer Memotext Study ID, Randomization arm and phone number of newly randomized participant. Memotext to activate enrollment by sending start-text to participants in **both arms**

Local coordinators: Collect HbA1c lab-reported value no later than 6 months prior to enrolment date, emergency department and hospitalization data, and OHIP/RAMQ numbers to link to admin data

Memotext: sends SMS of baseline questionnaires as URLs that linkout to REDCap for: KiT demographic Survey ,READDY, BDA Stigma Subscale, and SEDM **to both arms**

Intervention Start

Memotext: based on READDY tool responses, sends SMS of T1D-related questions, support, and management **to only intervention arm for 12 months. Both groups receive usual medical care during intervention period.**

6-Month

Follow-up assessments: Memotext sends SMS of 6-month questionnaires as URLs that linkout to REDCap: KiT Survey, READDY, BDA Stigma Subscale, SEDM **to both arms.** Interim Process Evaluation with intervention arm

12-Month

KiT intervention modification: based on results of process evaluation; adjustments or modification to KiT algorithm will be made to improve message and content delivery, and improve user engagement and satisfaction

Final Follow-up assessments: Memotext sends SMS of 12-month questionnaires as URLs that linkout to REDCap: KiT Survey,READDY, BDA Stigma Subscale, and SEDM **to both arms.** Process Evaluation, Health System utilization and Cost of implementation analysis performed at end of intervention.

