An additional secondary, exploratory objective is to conduct an **embedded process evaluation**. The process evaluation will occur during the delivery of the intervention, real-time engagement metrics will be analyzed to evaluate participant engagement and will allow for intervention modification to increase and improve user engagement and content delivery. The objectives of the process evaluation are to evaluate how and why the intervention achieved (or failed to achieve) the desired effects in order to gain an in-depth understanding of whether the intervention was received as intended, the mechanisms of action, and the conditions and factors associated with initial engagement and sustained use of the intervention. Additionally, we would like to identify the different paths of engagement (i.e., combinations of KiT components) that produce a positive effect on trial outcomes. Overall, the embedded process evaluation will optimize the engagement with the intervention and assess the feasibility of implementing this intervention in the real-world.

OBJECTIVES	ENDPOINTS	JUSTIFICATION FOR ENDPOINTS
Primary		
Compare the effectiveness of a digital T1D transition platform that will personalize transition education and support, as an adjunct to usual T1D transition	Self-efficacy for diabetes management measured by the Stanford self-efficacy for Diabetes Management scale (SEDM) at baseline, 6 months, and 12 months. The SEDM is an 8-item measure answered on a Likert scale from 1 (not at all confident) to 10 (totally confident), how confident they feel that they can carry out the listed tasks regularly at the present time. The	Validated and reliable ($\alpha = 0.90$); shown to have good internal consistency and test-retest validity; measure used in adolescents with type 1 diabetes(38,39); measure of self-efficacy related to core elements of diabetes self-management in

OBJECTIVES	ENDPOINTS	JUSTIFICATION FOR ENDPOINTS
care versus usual transition care alone on diabetes self-efficacy	score is calculated using the mean of the eight items with higher scores indicating self-efficacy. Minimal clinically important difference is 10%	adolescents with type 1 diabetes
Secondary		

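### The baseline SEDM, a covariate of the primary model, is rated only after the participant knows the arm, so a reaction to the allocation would bias the effect in an unknown direction

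*Protocol*

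**What the plan says.** Protocol section 5.4 sets the order of events. Consent is taken at step 5 and a study ID assigned at step 7. At step 8 the coordinator randomises, and "Both the local coordinator and participant will be aware of what study arm they were assigned to". Only at step 10, after an enrolment text, does the baseline survey go out: "The following SMS will include the first URL link to a REDCap survey that first prompts to participant to complete the baseline KiT survey". The SEDM is third in that chain, after the KiT survey and READDY and before the BDA stigma subscale. Non-responders get up to two reminders a week apart, then: "At week three, the local research coordinator will be notified via email by Memotext that the participant has not yet completed their questionnaires". No closing date for the baseline is given.

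The schema (section 1.1) shows the same order, with randomisation first and then, under baseline, "Memotext: sends SMS of baseline questionnaires as URLs that linkout to REDCap for" the SEDM among others. Table 1 (section 1.2) puts randomisation at -1 week and the SEDM at 0.

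Section 4.2 states that "This study is not blinded and therefore the research team, Memotext and participant will know which arm they have been randomized to". The primary endpoint table in section 3 describes the SEDM as asking "how confident they feel that they can carry out the listed tasks regularly at the present time". Section 8.5.2 compares 12-month SEDM between arms in a Bayesian linear model with baseline SEDM as a covariate. It declares benefit when the posterior probability exceeds 95%, and sets 0.75 points as the threshold for clinically important benefit.

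**The concern.** Baseline adjustment is safe because a covariate measured before randomisation cannot depend on the arm. Here the covariate is a subjective rating given after the participant has been told the arm. Someone allocated to KiT may feel more confident, or may rate themselves lower in expectation of help. Someone allocated to usual care may be disappointed. Any such difference enters the covariate, and the model removes it from the treatment contrast as if it were a pre-existing difference.

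If the recorded baseline is raised in the intervention arm, benefit is understated. If it is lowered, benefit is overstated and a false crossing of the 95% rule becomes more likely. Once the data are collected this way, a reaction to the allocation cannot be told apart from chance imbalance.

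Return of the baseline could also differ by arm, because completing it opens the intervention for one arm only: "If the participant is in the intervention arm, after they complete the baseline questionnaires, they will then be sent an SMS with a link", and "Once the enrolment survey is completed, the intervention will begin for those participants". Section 7.3 counts a participant who never completes the baseline SEDM and cannot be reached as lost to follow-up, so non-return is a loss after randomisation.

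**Working it through.** The protocol gives no figure for this point that could be reproduced. The check is of the sequence, then of what a reaction would do to the estimate.

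**Sequence.** Sections 1.1, 1.2, 5.4 and 6.2 agree that randomisation and disclosure follow consent directly and that the SEDM comes later. No section provides an SEDM before disclosure.

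**Bias formula.** Let *b* be the within-arm slope of 12-month on baseline SEDM, *d* the intervention-minus-control difference in recorded baseline caused by knowing the arm, and τ the total effect of allocation on the 12-month score. The adjusted estimate is the difference in 12-month means minus *b* times the difference in baseline means. A baseline taken before disclosure has expected difference 0, so the estimate is τ in expectation. A baseline taken afterwards has expected difference *d*, so the estimate is τ − *b·d*. The bias is −*b·d*.

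**Assumed values.** The protocol gives neither *b* nor *d*. Size of the bias in SEDM points (sign opposite to *d*):

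| Slope *b* | \|*d*\| = 0 | 0.1 | 0.2 | 0.3 |
|---|---|---|---|---|
| 0.4 | 0 | 0.04 | 0.08 | 0.12 |
| 0.5 | 0 | 0.05 | 0.10 | 0.15 |
| 0.6 | 0 | 0.06 | 0.12 | 0.18 |

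For non-zero shifts the smallest is 0.04/0.75 = 5.3% of the threshold and the largest 0.18/0.75 = 24.0%.

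**Simulation.** 20,000 trials per scenario, 93 per arm (117 × 0.8 = 93.6), linear regression on arm and recorded baseline, with the shift not carried into the 12-month score. SDs of 1.0 and 1.8 gave the same mean estimates to 0.01.

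| *b* | *d* | True effect | Adjusted | Unadjusted |
|---|---|---|---|---|
| 0.5 | +0.2 | 0.75 | 0.65 | 0.75 |
| 0.5 | −0.2 | 0.75 | 0.85 | 0.75 |
| 0.5 | −0.2 | 0 | 0.10 | 0.00 |
| 0.6 | +0.3 | 0.75 | 0.57 | 0.75 |
| 0.6 | −0.3 | 0.75 | 0.93 | 0.75 |

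**False declarations.** These depend on the SD, which is not given. Section 8.3 claims more than 80% power for 0.75 after 20% loss. By normal approximation, two-sided 5% (sidedness assumed), that implies an SD of at most 0.75 × √(93.6/2) / (1.96 + 0.84) ≈ 1.83; the exact t-test gives about 1.82. A separate simulation (SD 1.8, *b* = 0.5, 94 per arm, 4,000 runs, normal approximation to a flat-prior posterior, no true effect) met the 95% benefit rule in about 5% of runs at *d* = 0 and about 14% at *d* = −0.25. For the same shift and slope, a smaller SD would make the increase larger. These are illustrations, not estimates for this trial.

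**The case against.** The strongest reply concerns persistence. Participants stay unblinded and answer the same scale at 12 months, so a reaction might last. If a share *c* of the shift carries over, the adjusted bias relative to the intervention's own effect is (*c* − *b*)*d* and the unadjusted bias is *c·d*. With *c* = 1, *b* = 0.5, *d* = +0.2 and no intervention effect, the adjusted estimate is 0.5 × 0.2 = +0.10 and the unadjusted +0.20. On that target the sign reverses and dropping the covariate does worse.

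The algebra is right but it changes the target. The planned intention-to-treat contrast is the total effect of allocation, which in that example is 0.20. The adjusted model understates it by *b·d* = 0.10 and the unadjusted contrast recovers it. A lasting reporting reaction is a general limitation of an open trial with a self-rated endpoint; a baseline taken after disclosure adds a separate, avoidable error. What stands is that disagreement between the two models would not by itself show the cause.

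Other points stand as limits. The sizes are assumed and zero is possible. Same-day completion is possible, so a delay of weeks describes slow responders. Incentives and reminders are equal across arms, and KiT content starts only after the baseline, so only knowledge of the arm can act. Differential return is a possibility, not a finding.

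Section 4.2 says the lack of blinding of the research team will cause no bias, but it rests this on the concealed sequence. Concealment protects who enters each arm, not how an informed participant then answers.

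**Conclusion.** The concern holds and should be fixed. The protocol consistently collects a self-rated covariate of the primary model after disclosure of the arm. Any between-arm reaction biases the adjusted effect of allocation by −*b·d*, in a direction that cannot be predicted. Under the assumed slopes and shifts this is 0.04 to 0.18 points, 5% to 24% of the 0.75 threshold; without a reaction it is nil. The document shows no actual imbalance, so confidence that the result will be materially affected is moderate. The matter cannot be left to a SAP, because no analysis can recover a baseline from before disclosure.

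**What to change.** **Participants not yet randomised.** In section 5.4, collect at least the baseline SEDM by REDCap link after consent (steps 5 to 7) and before step 8, and randomise and release the allocation only once it is submitted. Align the schema and Table 1. The means exist: the study ID is assigned at step 7, a valid email address is an inclusion criterion (section 5.1), so those who consent on paper can also be sent the link, and coordinators can already track baseline completion in REDCap (section 10.1.6.1). READDY, which steers KiT content, can stay in the step 10 survey. Consenters who never return the SEDM become screen failures as section 5.3 defines them, not losses after randomisation.

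**Participants already randomised.** Keep everyone in the primary analysis. Report by arm the baseline SEDM, its return, and the days from randomisation to return. Add a sensitivity analysis of the primary model without the baseline SEDM covariate, read as a check on the allocation effect and not as a diagnosis of the cause of any difference.

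**Cost.** An amendment and a reordered REDCap step. The chained survey must be split, and with it the gift-card trigger, which now fires only when all questionnaires of a time-point are complete (section 6.1.1). Some consenters will not be randomised. Section 9 shows that enrolment is under way and the number still to be randomised is not stated, so the change may reach only part of the sample and leaves two cohorts with differently timed baselines. The sensitivity analysis is less precise than the primary model.
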